7.7.3. COVID-19-like Signs and Symptoms

If a participant experiences COVID-19-like symptoms (eg, cough, feverishness, dyspnea, gastrointestinal symptoms, anosmia), the following should take place:

- Participants should contact the study site at the time of symptom onset
- A nasal swab should be collected from the participant at home (using available material for home swabs) as soon as possible and preferably no longer than 2 to 3 days after the onset of symptoms and stored appropriately. It is preferred that the swab is taken by a caregiver (spouse, partner, relative, friend, or health care professional). If that is not possible, the participant can collect the swab him- or herself. The sample should be transferred to the study site by an appropriate method as soon as possible after being collected. A second nasal swab will be obtained 2 to 4 days after the first swab following the same procedures as the first nasal swab or at the study site if appropriate procedures are in place.

The presence of SARS-CoV-2 infection and influenza infection will be assessed at the study site by molecular testing using the nasal swab sample.

- Participants should complete the Symptoms of Infection with COVID-19 (SIC) and record their highest body temperature daily starting on the first day they experience symptoms. If either nasal swab is positive for SARS-CoV-2 or influenza, collection of data will continue until sign and symptom resolution. If the first nasal swab is negative, collection of data will continue until the negative test is confirmed by the second nasal swab.
- For participants with a positive test result for SARS-CoV 2 infection, a study visit will be conducted 28 days after symptom onset to assess the clinical course of the infection, record concomitant medications since symptom onset, and obtain a blood sample for evaluation of the immune response and other biomarkers.

The SIC asks participants to indicate, for each of 25 symptoms and on a daily basis, whether or not they experienced the symptom (Yes/No), and if Yes, to rate the severity (on an 11-point scale ranging from 0 to 10, where 0 = none to 10 = worst). In addition, 4 questions are asked that are asked to be responded to by Yes/No, without severity assessment.

The presence of SARS-CoV-2 infection and influenza infection will be assessed at the study site by molecular testing using the nasal swab sample.

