The number and percentage of participants with at least one positive non-S protein ELISA (e.g., N ELISA), if available, will be tabulated by vaccine regimen. The analysis will be repeated pooling all active regimens vs. placebo, where data from all cohorts will be pooled. If at least 5 positive non-S protein ELISA events have been observed, VE can be calculated against this endpoint, using the same approach as outlined above for the VE against molecularly confirmed SARS-CoV-2 infection.

For each participant with confirmed COVID-19 infection, a narrative will be prepared based on the visit performed 28 days after the onset of COVID-19 signs and symptoms and other selected information from the clinical database, as available:

- participant ID
- vaccination regimen
- sex, race, ethnicity, age, BMI, dates at which vaccinations were received
- physical examination findings based on the visit performed 28 days after the onset of COVID-19 signs and symptoms
- vital signs including body temperature based on the visit performed 28 days after the onset of COVID-19 signs and symptoms
- concomitant medications since symptom onset
- Humoral immune responses as collected at the planned time points + those obtained from the blood sample taken on the visit performed 28 days after the onset of COVID-19 signs and symptoms. This information may be presented graphically.

For the analysis of the SIC (Patient Reported Outcomes, PRO) data, the following considerations apply

- An “episode” is defined as a period in which any symptoms are reported on the SIC, starting from the first day on which symptoms were reported until the first day that the PRO was not completed because the symptoms had resolved (this will be indicated in the SDTM data, with reason for not completing the PRO = “Symptoms resolved” (or similar) or death)
- A symptom (e.g. feeling generally unwell, fatigue, physical weakness, cough, etc.) is assumed to be present on each day the associated Yes/No question is answered “Yes” or the associated severity question has a rating > 0 .

- If the PRO was not completed due to the participant being too ill or due to the participant being hospitalized, the symptom will be considered present with severity score 10. If the PRO was not completed due to any other reason, no imputations will be done.

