Duration of the episode will be calculated as episode end date – episode start date. Duration of each symptom will be calculated as last day of symptom reporting – first day of symptom reporting + 1. Duration of the maximum severity is defined as the last day of reporting the maximum severity – the first day of reporting the maximum severity + 1.

The following analyses will be conducted for confirmed SARS-CoV-2 infection cases and confirmed influenza infection cases separately:

- At the level of first episodes, the following statistics will be calculated: number of episodes, mean and median duration of episodes (with min, max, q1 and q3), and mean and median number of symptoms reported per episode (with min, max, q1 and q3).
- At the level of the symptoms for each first episode, the following statistics will be calculated: number of participants experiencing the symptom, mean and median duration of each symptom (with min, max, q1 and q3), median (with q1 and q3) of maximum severity of each symptom, median duration of the maximum severity of each symptom (with min, max, q1 and q3).
- At the level of the participants, for each episode and each symptom separately, the duration, and minimum and maximum severity scores will be tabulated (as available).

In addition, participant listings will be provided containing the SIC information for each time point.

More details about these analyses will be provided in the DPS.

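### The SIC episode ends only at a 'Symptoms resolved' skip or death, so completed symptom-free diary days before that record are counted as illness

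*SAP*

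**What the plan says.** All the rules are in SAP section 7.7.3.

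- **Concept and start of an episode:** "An “episode” is defined as a period in which any symptoms are reported on the SIC, starting from the first day on which symptoms were" (sentence cut here); day one is thus the earliest diary day with a symptom entered.
- **End of an episode:** it runs "until the first day that the PRO was not completed because the symptoms had resolved". The SAP adds that this is read from the recorded reason for non-completion, which is 'Symptoms resolved' (or similar) or death.
- **Episode duration:** "Duration of the episode will be calculated as episode end date – episode start date".
- **Single-symptom duration:** "Duration of each symptom will be calculated as last day of symptom reporting – first day of symptom reporting + 1".
- **Presence on a day:** a symptom "is assumed to be present on each day the associated Yes/No question is answered “Yes” or the associated severity question has a rating" above zero. A diary not completed because the participant was too ill or in hospital counts as symptom present with severity 10. Diaries missing for any other reason are not imputed.
- **When collection stops:** if either swab is positive, "collection of data will continue until sign and symptom resolution". Otherwise: "If the first nasal swab is negative, collection of data will continue until the negative test is confirmed by the second nasal swab". On timing: "A second nasal swab will be obtained 2 to 4 days after the first swab".

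Episode duration is summarised by mean, median, range and quartiles for first episodes, separately for confirmed SARS-CoV-2 and confirmed influenza cases. It is also tabulated per participant.

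**The concern.** The two halves of the episode definition rest on different things. The opening half depends on symptoms being reported, while the closing half depends on why a form was not filled in. The SIC is a daily Yes/No form, so a participant can complete it and answer 'No' throughout. Under the SAP's own presence rule that is a symptom-free day, yet nothing in the section lets it end the episode. Only a later skip with the right reason, or death, does so.

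The plan can produce such days. After a negative first swab, diaries continue to the second swab whether or not symptoms persist. If the second swab is positive, the participant is a confirmed case and enters the episode analysis.

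A second gap follows from the same rule. If no 'Symptoms resolved' record exists and the participant did not die, the definition gives no end date.

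At stake is a duration that partly reflects how a participant used the diary rather than how long the illness lasted. The error can only lengthen the episode relative to its symptomatic span.

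**Working it through.** The SAP gives no numerical duration to reproduce, so the check is a day count.

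**Inputs.** Day 1 is the first symptomatic day (start rule). *S* is the last symptomatic day (presence rule). *k* is the number of completed all-'No' diaries between day *S* and the first 'Symptoms resolved' skip. The SAP gives no value for *k*; the values below are assumed.

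**Step 1: duration under the SAP rule.** The skip falls on day *S* + *k* + 1. End minus start is (*S* + *k* + 1) − 1 = *S* + *k*.

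**Step 2: symptomatic span.** Applying the SAP's inclusive single-symptom formula from first to last symptomatic day gives *S* − 1 + 1 = *S*.

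**Step 3: excess.** (*S* + *k*) − *S* = *k* days.

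| Last symptomatic day *S* | *k* = 0 | *k* = 1 | *k* = 2 | *k* = 3 |
|---|---|---|---|---|
| 5 | 5 (exact) | 6 (+20%) | 7 (+40%) | 8 (+60%) |
| 10 | 10 (exact) | 11 (+10%) | 12 (+20%) | 13 (+30%) |

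For *S* = 5 and *k* = 3, the diaries on days 6 to 8 are all-'No', the skip is on day 9, and 9 − 1 = 8.

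**Step 4: how far the two-swab route reaches.** The first swab is preferably taken no later than 2 to 3 days after onset, so by day 1 + 3 = 4. The second follows 2 to 4 days later, so by day 4 + 4 = 8. For an illness ending on day 5, all-'No' diaries on days 6 to 8 need the latest day of both windows. An illness ending on day 10 is still symptomatic at day 8, so this route adds nothing to it. The SAP does not give the time to a swab result, and the first window is only a preference.

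**Step 5: check of the correction.** With the end date on day *S* + 1 and the formula unchanged, duration is (*S* + 1) − 1 = *S* for every *k*. Moving the end date to day *S* itself without adding 1 would give *S* − 1, one day short in every episode.

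**The case against.** The strongest defence is that the rule works in the case it was written for. Swab-positive participants stop the diary at resolution, so the first skip should fall on the day after the last symptom. The episode formula has no + 1, and that fits an end date one day past the last symptomatic day. This stands: at *k* = 0 the result is exact.

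It is also fair that the opening half of the definition excludes symptom-free days in concept. But the end marker is explicit and is what a programmer would implement, so the opening words do not rescue the derivation.

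The two-swab route is narrow. It needs a negative then a positive swab, recovery in between, and completed all-'No' diaries rather than a 'Symptoms resolved' skip, which nothing bars between swabs. That limits how often the problem arises but does not remove it, since the daily form allows an all-'No' entry in any participant.

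A reader might infer several stronger things that the document does not support:

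- **That a constant number of days is added, shrinking relative differences.** Three days added to both 5 and 10 would give 8 against 13, moving the ratio from 0.50 to 0.62. The two-swab timing does not add three days to a 10-day illness, and section 7.7.3 plans no comparison of durations between regimens.
- **That days missed for other reasons are symptom-free.** Their status is unknown, so counting them as overstatement would be a guess.
- **That an episode longer than any one of its symptoms is an error.** Fever on days 1 to 3 and cough on days 4 to 10 properly give a longer episode than either.

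Finally, section 7.7.3 leaves further detail to the DPS, which is not available here. The end rule itself is fixed in the SAP, so it should be corrected there.

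**Conclusion.** The point holds as a conditional error in a stated derivation. Episode duration exceeds the symptomatic span by exactly the number of completed all-'No' diaries before the 'Symptoms resolved' record, and by nothing if there are none. It would be wrong to conclude that duration is always overstated.

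The size rests on an assumed *k*. For 5 symptomatic days and *k* of 1 to 3 the excess is 20% to 60%; the SAP gives no frequency from which to estimate an average effect.

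The importance is modest. Section 7.5 lists the presence and severity of COVID-19 signs and symptoms as exploratory, section 7.7.3 plans descriptive statistics only, and nothing in the SAP makes episode duration a headline result. Listings of SIC data by time point would also let a reader see trailing all-'No' days. The correction is still worth making: it removes a conflict within the definition, supplies a missing end date, and leaves every episode with *k* = 0 unchanged.

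**What to change.** In section 7.7.3, keep each episode bounded as now by the first 'Symptoms resolved' record or death, and change only the end date used for duration:

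1. Set the end date to the day after the last day within the episode on which any symptom is present under the SAP's rules. Include days imputed with severity 10 because the participant was too ill or hospitalised, so that severe episodes are not cut short.
2. Keep duration as end date minus start date.
3. Use the same end date when no 'Symptoms resolved' record exists, and flag the episode as not confirmed closed if no all-'No' diary follows the last symptomatic day.
4. Keep death as a closing event.
5. Flag trailing days missed for other reasons rather than reclassifying them as ill or well.

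The cost is a few sentences in the SAP and one change to the derivation. No new data are needed.

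### On its plain reading, the SIC rule makes all 25 rated symptoms present at severity 10 on any diary day missed through illness or hospitalisation, including symptoms never reported

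*SAP*

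**What the plan says.** All of this is in SAP section 7.7.3.

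- **Instrument.** The SIC is answered "for each of 25 symptoms and on a daily basis". Each symptom is a Yes/No item and, if Yes, is rated "on an 11-point scale ranging from 0 to 10, where 0 = none to 10 = worst". A further "4 questions are asked that are asked to be responded to by Yes/No, without severity assessment".
- **Completed day.** A symptom "is assumed to be present on each day the associated Yes/No question is answered" Yes, or its severity rating is above 0. This works item by item.
- **Missing day.** The trigger concerns the whole questionnaire: "If the PRO was not completed due to the participant being too ill or due to the participant being hospitalized". The consequence is stated for "the symptom" of the bullet before: if the gap is "due to the participant being hospitalized, the symptom will be considered present with severity score 10". A gap for any other reason is not imputed. The rule does not ask whether the symptom was reported on another day, or why the participant was in hospital.
- **Outputs.** For SARS-CoV-2 and influenza cases separately, the SAP tabulates how many participants had each symptom, the median of its maximum severity, its duration and the duration of its maximum. Per episode it gives "mean and median number of symptoms reported per episode (with min, max, q1 and q3"). No version without imputation is planned. Further detail is left to the DPS, which is not shown.

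Section 7.5 lists the presence and severity of COVID-19 symptoms among the exploratory endpoints.

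**The concern.** Giving the worst score to a symptom that a participant has reported, on a day when they are too ill to answer, is a recognised and defensible convention. This rule goes further. A hospital day indicates severe illness but not which symptoms were present. Yet the rule records loss of smell or a gastrointestinal symptom as present at the maximum in someone who never mentioned it.

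What is at stake is the symptom profile of confirmed cases. Rare symptoms are affected most, because an imputed case adds one to the frequency of every symptom. Maximum severity is pulled towards 10 in proportion to the share of imputed participants. The tables would then partly describe how many participants had an unanswered diary in hospital, and a reader could not separate that from real symptoms.

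**Working it through.** The SAP gives no figure on this point, so there is nothing to reproduce. The check is a reading of the rule followed by arithmetic. The only inputs from the SAP are the 25 rated symptoms, the 0 to 10 scale and the imputed score of 10. Case numbers, imputed shares, symptom counts and reported severities are all assumptions.

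**Step 1: scope of the rule.** On a completed day, presence is decided symptom by symptom. On a missed day, the trigger is the whole form, so every item is missing at once. The symptom referred to is any SIC symptom, as in the preceding bullet, and no clause narrows it. Applied literally, each of the 25 becomes present at 10. The 4 unscored items cannot take a score of 10, and the SAP does not say whether they are set to present.

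**Step 2: one participant.** Assume a 10-day episode with *k* symptoms reported at severity 5 and at least one imputed day. Symptoms added = 25 − *k*. The result is the same for 1 or 3 imputed days.

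| Reported *k* | Present, as written | Added | Present, limited to reported symptoms | Present, no imputation |
|---|---|---|---|---|
| 3 | 25 | 22 | 3 | 3 |
| 6 | 25 | 19 | 6 | 6 |
| 10 | 25 | 15 | 10 | 10 |
| 15 | 25 | 10 | 15 | 15 |

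Maximum severity of the symptoms shown as present is 10 as written, 10 under the limited rule and 5 with no imputation.

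**Step 3: frequency of a symptom.** With *m* episodes, *g* of them imputed, and true frequency *q*, the displayed frequency is *g/m* + (1 − *g/m*) × *q*.

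| *g* of *m* | *q* = 10% | *q* = 30% |
|---|---|---|
| 1 of 20 | 0.05 + 0.95 × 0.10 = 14.5% | 0.05 + 0.95 × 0.30 = 33.5% |
| 2 of 10 | 0.20 + 0.80 × 0.10 = 28% | 0.20 + 0.80 × 0.30 = 44% |
| 3 of 5 | 0.60 + 0.40 × 0.10 = 64% | 0.60 + 0.40 × 0.30 = 72% |

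**Step 4: maximum severity.** Suppose one participant reports a symptom at 3 and one other participant is imputed. If the summary is taken over those who have the symptom, the table shows 2 participants and a median maximum of (3 + 10)/2 = 6.5. This is an extreme case, a symptom with a single true report.

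**Step 5: symptoms per episode, only if imputed symptoms are counted.** Assume 8 symptoms per case and one imputed case.

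- 5 cases: mean (4 × 8 + 25)/5 = 11.4 instead of 8.0.
- 10 cases: mean (9 × 8 + 25)/10 = 9.7 instead of 8.0.
- In both, the median and both quartiles remain 8 and the maximum becomes 25.

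Whether this step applies is open. The count is of symptoms *reported*, and the durations run between days of *reporting*. An imputed day is arguably neither.

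**The case against.** The case against has several parts.

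- **Loose drafting.** The sentence is in the singular, the number 25 does not appear in it, and the DPS may narrow it. This stands in part: the scope is a reading, though the natural one, and the SAP itself contains no restriction.
- **True state unknown.** A reader might infer that the rule invents symptoms the participant never had. The documents do not support that, because a symptom may have arisen on the missed day. What can be said is that it was never reported.
- **Counts and durations.** A reader might infer that these are certainly inflated. The wording about reported symptoms and reporting days leaves that open. Even if counts are affected, the planned median and quartiles do not move in the example, and a maximum of 25 would be conspicuous. This stands.
- **Case numbers.** The SAP forecasts neither the number of cases nor the share hospitalised. The 5 and 23 events in section 7.7.3 are thresholds for calculating or powering vaccine efficacy. This stands, so no claim is made that a few hospitalised participants will dominate the tables.
- **Unrelated admissions.** The text does not exclude them, but the summaries cover only confirmed SARS-CoV-2 or influenza episodes, so such admissions should be uncommon.
- **Traceability.** Participant-level tables and SIC listings are planned, so affected participants should be identifiable. That helps a careful reader but does not correct the summary tables.
- **Conservatism.** Worst-score imputation is a legitimate choice, and restricting it has a bias of its own: someone hospitalised early may show few symptoms. This is a real cost of the remedy. It does not justify imputing symptoms with no report behind them.

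**Conclusion.** The point holds in a limited form. As written, a single diary day missed through illness or hospitalisation makes all 25 rated symptoms present at severity 10, and the severity part is undefined for the 4 unscored items. The per-symptom frequency and the median maximum severity are plainly affected. The symptom count and durations may or may not be, and the SAP should settle this.

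The size depends on the assumed share of imputed episodes. For a symptom with 10% true frequency, the displayed figure runs from 14.5% (1 of 20 imputed) to 64% (3 of 5).

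A reader might go on to doubt the efficacy results. The documents give no ground for that: the SIC summaries are descriptive and exploratory, and no primary, secondary or vaccine efficacy analysis uses the imputed values. The priority is low.

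**What to change.** Amend the imputation bullet in section 7.7.3 and carry it into the DPS:

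1. Impute presence and severity 10 only for symptoms the participant reported on at least one day of that episode. Leave never-reported symptoms missing.
2. State that imputed days do not count as reported days for symptom counts and durations.
3. State how the 4 unscored items are handled on such days.
4. Show the per-symptom frequency and maximum-severity tables also without imputation. This is needed even after item 1, because reported symptoms still receive a maximum of 10 from the rule.
5. Give, on a separate line, the number of participants and days with the questionnaire missing because the participant was too ill or hospitalised.

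The cost is a few sentences, a small change to the derivation and one extra version of two tables. The downside is that symptoms first arising in hospital are not captured, and participants hospitalised early may show few symptoms although they are among the sickest. The separate line makes both visible.

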7.7.4. Definition of Subgroups

Selected safety and immunogenicity analyses will be conducted by the seropositivity status (positive vs. negative) of the participant. A participant will be considered seropositive if:

1. The serological test for SARS-CoV-2-specific antibodies at baseline (if available) is positive

Note: in case multiple test results are available (IgG, IgM, IgA, no isotype specified), then as soon as one of the test results is positive, the participant will be considered seropositive.

OR

2. The S ELISA immunogenicity readout on Day 1 is considered positive.

At the time of first interim analysis of a cohort, S ELISA Day 1 data for that cohort may not be available at the time of the CRF database snapshot or lock. In that case, participant serostatus will be based solely on the serological test for SARS-CoV-2-specific antibodies at baseline. As of the second interim analysis, it is expected that S ELISA Day 1 data will have become available for the participants, so that both criteria can (and will) be applied.

